This is a single center, randomized; singe blinded, two-arm trial comparing the effects of direct placement of LPT over the spared neurovascular bundles vs. standard care (no placement of tissue) on erectile recovery and quality of life in patients undergoing bilateral nerve sparing radical prostatectomy for prostate cancer.

VCUT for Erectile Recovery During Bilateral Nerve Sparing RRP Protocol												
	Consult	Baseline Eval	Surgical Day	Post Op Day 1	2 weeks Post Op	1 Month Post Op	3 months Post Op	6 months Post Op	9 months Po	12 months Post Op	18 Months Post Op	
Informed Consent	x											
Medical Clearance		x										
IIEF	x				x	x	x	x	x	x	x	
SEQ	x				x	x	x	x	x	x	x	
EPIC, SF12, AUA SI	x				x	x	x	x	x	x	x	
Randomization	x											
Rx (PDE5i)					x							
AE Monitoring		x	x	x	x	x	x	x	x	x	x	
PSA Monitoring						x						

The sample size will be 10 patients randomized to each study arm (20 patients total). Study procedures will involve screening and informed consent after initial consultation, baseline evaluation including medical clearance and completion of validated questionnaires, and randomization.

In order to minimize the need for research-only in-person visits, telemedicine visits may be substituted for in person clinical trial visits or portions of clinical trial visits where determined to be appropriate and where determined by the investigator not to increase the participant's risks. Prior to initiating telemedicine for study visits the study team will explain to the participant, what a telemedicine visit entails and confirm that the study participant is in agreement and able to proceed with this method. Telemedicine acknowledgement will be obtained in accordance with the Guidance for Use of Telemedicine in Research. In the event telemedicine is not deemed feasible, the study visit will proceed as an in-person visit. Telemedicine visits will be conducted using HIPAA compliant method approved by the Health System and within licensing restrictions

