The occurrence of any serious adverse effects will end the patient's participation in the study and halt enrollment in the study to determine the safety of continuing the study. Each and every possible adverse effect of LPT will be investigated and treated individually to minimize the participant's discomfort. The safety of having the individual complete the study will also be assessed on an individual basis. At any time the participant can decide to terminate his participation in the study and no penalty or loss of benefits to which they are entitled.

The risks of radical prostatectomy will apply to both groups. These include but are not limited to bleeding, infection, and injury to surrounding structures. Rare complications include rectal injury requiring fecal diversion and acute blood loss anemia requiring transfusion. An ejaculation is expected. Late complications include urinary incontinence, erectile dysfunction, urethral stricture disease, and bladder neck contracture.

7. Confidentiality

Paper consent forms, enrollment check sheets, and other source or study documentation will be kept in a study binder. This binder will be stored in a locked office available only to the study team. Electronic data will be housed in a secure password protected REDCap database maintained by the Data Informatics Services Core within the Johns Hopkins Biostatistics Center. Only the study team will have access to this secure database. Of note, to maintain the protected health information of patients enrolled in this study, only the study Principal Investigator and primary coordinators will have the ability to export data containing identifying information from this master database. For the purposes of analysis, only de-identified data will be exported.

8. Benefits

The patient's conditions may improve as a result of participation in this study, specifically as related to erectile function and quality of life. However, there is no guarantee of this. The information from this research study may lead to a better treatment in the future for people with prostate cancer. The patients may not benefit from participation in this study. Their conditions may not get better or may become worse while they are in this study.

9. Payment and Remuneration

There will be no payment or remuneration for the participants in this study.

10. Costs

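### Section 6 leaves unclear whether a serious adverse event ends a man's study follow-up, and nothing in the protocol secures later data collection or an as-randomised analysis

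*Combined protocol and SAP*

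**What the plan says.** Section 6 (Risks) of the combined protocol and SAP has one paragraph on what follows an adverse effect. Its sentences run in this order:

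- The automatic rule, which opens "The occurrence of any serious adverse effects will end the". What ends is the man's participation, and the same sentence pauses recruitment while safety is reviewed.
- Handling of effects of the tissue: "Each and every possible adverse effect of LPT will be investigated and treated individually".
- Case-by-case assessment: "The safety of having the individual complete the study will also be assessed on an individual basis".

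The next paragraph turns to surgery: "The risks of radical prostatectomy will apply to both groups". It continues: "Rare complications include rectal injury requiring fecal diversion and acute blood loss anemia requiring transfusion". It then adds: "Late complications include urinary incontinence, erectile dysfunction, urethral stricture disease, and bladder neck contracture".

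Three other places bear on this:

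- Section 2 describes a single placement of tissue during the operation, compared with none. Its visit table schedules questionnaires and the row "AE Monitoring" out to 18 months.
- Section 5 (Study Statistics) sets the primary outcome as the IIEF erectile function domain at 1, 3, 6, 9, 12 and 18 months. It sizes the trial on the 6-month score. It names ANOVA and says the planned number allows for dropout, without giving a rate. It names no analysis population and no method for missing scores.
- Section 6 also says that the questionnaires and Stravix are the only parts of the protocol outside standard care.

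**The concern.** An automatic exit and an individual assessment cannot both govern the same event unless they differ in scope, and no scope is given. A coordinator could not tell from the text whether a transfusion in a control-arm patient ends his participation.

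In a drug trial, ending participation may at least stop exposure. Here the exposure is a one-time implant. Once it is placed, the study-specific activity left to end is follow-up.

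The men affected would be those with serious events, whose later course matters most for a donor-tissue product. Section 6 lists disease transmission and immune rejection among the risks of the tissue. The late complications it names include erectile dysfunction, which the primary outcome measures. If these men leave the record early, the trial loses safety information and primary-outcome data in a group selected by what happened after randomisation.

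**Working it through.** **1. The sentences side by side.** At least two readings fit.

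- Reading A: every serious event, in either arm, ends participation, and individual assessment applies only to non-serious effects.
- Reading B: individual assessment qualifies the rule, so some men with serious events complete the study.

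A second ambiguity crosses these. The rule may cover all serious events or only those due to LPT, which is the subject of the sentence between. Under B nothing need be lost for a man who stays in. Reading A is the plain one, and the steps below follow it.

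**2. What is left to end.** After placement no exposure can be withdrawn. A serious event between randomisation and placement is different, because it could still prevent exposure.

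**3. Data lost per man.** Section 6 counts 6 further questionnaire administrations. The Section 2 table shows 7 after surgery (2 weeks and 1, 3, 6, 9, 12 and 18 months). The primary IIEF time points number 6, because Section 5 omits 2 weeks. The adverse-event row has 10 marks: baseline, surgical day, postoperative day 1, and 7 from 2 weeks on.

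| Serious event occurs | Primary IIEF points lost (of 6) | Questionnaire rounds lost (of 7) | AE checks lost (of the 7 from 2 weeks) |
|---|---|---|---|
| In hospital | 6 | 7 | 7 |
| Between the 1- and 3-month visits | 5 | 5 | 5 |
| Between the 3- and 6-month visits | 4 | 4 | 4 |

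Each row loses the 6-month score. These counts need no assumption beyond reading A.

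**4. Bias in the IIEF comparison.** Let p be the share of an arm removed and g the number of points by which removed men would score below retained men (T = LPT, C = control). Each arm's as-randomised mean is its retained mean minus p × g. Therefore

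retained difference − as-randomised difference = gT × pT − gC × pC.

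The documents give no event rates and no score gaps, so every input here is assumed.

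| Removal, T v C | Gap, T v C | Bias (points) |
|---|---|---|
| 10% v 10% | 10 v 10 | 1.0 − 1.0 = 0 |
| 2% v 1% | 10 v 10 | 0.2 − 0.1 = 0.1 |
| 10% v 10% | 15 v 5 | 1.5 − 0.5 = 1.0 |
| 20% v 10% | 10 v 10 | 2.0 − 1.0 = 1.0 |
| 20% v 10% | 15 v 5 | 3.0 − 0.5 = 2.5 |
| 10% v 20% | 15 v 15 | 1.5 − 3.0 = −1.5 |

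The design difference in Section 5 is 5 points, so 0.1 is 2% of it and 2.5 is half of it. The sign can go either way.

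**5. How many men.** Section 5 plans 30 per arm and Section 2 plans 10. At 2% v 1%, expected serious events are 30 × 0.03 = 0.9, or 10 × 0.03 = 0.3. At 20% v 10% they are 30 × 0.30 = 9, or 10 × 0.30 = 3. The upper figures would require enrolment to resume after repeated halts.

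**6. Cost of keeping these men in the analysis.** Section 5 states no SD. Its 23 per arm (5 points, one-sided 0.05, 80% power, two-sample t) implies an SD of 6.57 to 6.71, and 6.71 is used. Assume a 5-point effect in event-free men, a 10-point gap and 30 per arm. The as-randomised effect is 5 − 0.1 = 4.9 at 2% v 1%, and 5 − 1.0 = 4.0 at 20% v 10%. Simulated power (8,000 trials per setting), as randomised v with removal, is 0.864 v 0.878 and 0.642 v 0.822. The higher figures answer a question about event-free men only.

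**The case against.** The strongest reply is that the protocol says participation ends. It does not say that scores and adverse events stop being recorded. Under reading B a man may complete the study and no data are lost. This stands as far as it goes: the documents do not establish that follow-up stops. But no sentence says it continues, and the plain meaning of ending participation after a one-time implant is that study follow-up ends.

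Second, the event itself is not hidden. It is seen, it halts enrolment, possible LPT effects are to be investigated, and clinical care continues because only the questionnaires and Stravix lie outside standard care. This also stands. What is not assured is study capture of later events and later scores.

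Third, the bias may be negligible. At 2% v 1% with equal 10-point gaps it is 0.1 points, with fewer than one expected event across both arms. That is a fair reading of low event rates, but it is not a bound: the same formula gives 2.5 points under other assumed inputs.

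**Conclusion.** The point holds as unreconciled wording with a practical consequence. Section 6 contains two rules of unstated scope. On the plain reading, the stated rule would cost up to 6 of 6 primary time points, 7 of 7 questionnaire rounds and 7 scheduled adverse-event checks for a man with an in-hospital event. At 10 or 30 per arm, one such man is 10% or about 3% of his arm. The counts rest on the Section 2 table and on reading A. The wording should be changed.

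A reader might infer three stronger conclusions, which the documents do not support:

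- That follow-up certainly stops. The text is ambiguous, and the individual-assessment sentence may soften the rule.
- That the IIEF comparison is biased, or biased in favour of LPT. This depends on event rates and score gaps that are not given; the bias may be zero, positive or negative. The case therefore rests mainly on retained safety and outcome data.
- That men given androgen or radiation therapy after surgery are also removed, because Section 3 lists postoperative therapy among its exclusions. No removal rule is written, and the PSA monitoring in Section 2, with its recurrence definition, suggests that follow-up runs past recurrence.

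**What to change.** 1. Reconcile the Section 6 sentences and state which events and which arms each covers. This point takes no position on the safety rule or the enrolment halt, which are for the sponsor and the investigator.
2. State in Sections 2 and 6 that, separately from any safety decision, questionnaires and adverse-event collection continue to 18 months unless the man withdraws consent.
3. State in Section 5 that all randomised men are analysed in their assigned arm, and name the method for missing scores. Without such a method, an as-randomised analysis cannot be carried out once a score is missing.

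The cost is protocol wording and continued questionnaires for what is likely to be a few men. The statistical downside is dilution: men with complications stay in the comparison and may shrink the estimated effect. Under the assumptions in step 6 of the working, the power given up is about 0.01 at low event rates and 0.18 at the high, unequal rates. In exchange, the estimate applies to all men randomised.
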